3.7. Replacement of Subjects

Subjects enrolled and withdrawn from study any time prior to first dose of study drugs will not be considered evaluable for assessment and will be replaced with another subject. All subjects who have received a dose of study drugs will be included in an as treated analysis.

3.8. Prohibited Treatments

Medications intended solely for supportive care are allowed (i.e. antiemetics, analgesics, megestrol acetate for anorexia).

The following concomitant medications are prohibited:

- Concurrent systemic anticancer therapy with agents other than the combination study drug therapy (vidutolimod + cemiplimab) is not allowed at any time during the study. Topical anticancer therapy agents are allowed provided they are not used for the target or non-target lesions
- Agents known to have TLR9 antagonist activity are prohibited throughout the study. The current known antagonists are chloroquine, hydroxychloroquine, and quinacrine.
- Systemic pharmacologic doses of corticosteroids > 10 mg/day of prednisone equivalent are not permitted within 15 days of study enrollment. However, corticosteroid administration is allowed in the following circumstances:
 - In the treatment of subjects with known adrenal insufficiency (see Section 4.1.1.1). Consultation with the Medical Monitor is required prior to enrollment of subjects with adrenal insufficiency.
 - Replacement doses, topical, ophthalmologic, and inhalational steroids are permitted.
 - For the management of immune-mediated toxicities and for palliation of pain or cancer related complications during study conduct. Note: Treatment on study cannot be resumed while on systemic pharmacologic doses of corticosteroids > 10 mg/day of prednisone equivalent
- Complementary medications to treat the disease under study (e.g. herbal supplements or traditional Chinese medicines).

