- Severe uncontrolled medical disease within 12 months of Screening, including but not limited to poorly controlled hypertension, unstable angina, myocardial infarction, congestive heart failure (New York Heart Association Class II or greater), pericarditis, cerebrovascular accident, or implanted or continuous use of a pacemaker or defibrillator, or emphysema with $FEV1 \leq 50\%$ predicted.
- Known history of immunodeficiency.
- Known additional malignancy that is progressing or required active treatment within the past 3 years. Exceptions include cancers that have undergone potentially curative therapy, e.g. basal cell carcinoma of the skin, squamous cell carcinoma of the skin, localized prostate cancer with prostate-specific antigen level below 4.0 ng/mL, in situ cervical cancer on biopsy or a squamous intraepithelial lesion on Papanicolaou smear, and thyroid cancer (except anaplastic), in situ breast cancer, and adjuvant hormonal therapy for breast cancer > 3 years from curative-intent surgical resection.
- Active autoimmune disease that required systemic treatment in past 2 years; replacement therapy is not considered a form of systemic treatment.
- Untreated, symptomatic, or enlarging central nervous system metastases or carcinomatous meningitis (including leptomeningeal metastases from solid tumors).

Investigational product, dosage, and mode of administration:

Subjects will receive vidutolimod and cemiplimab, as follows:

1. Vidutolimod IT 10 mg weekly for 7 doses (W1D1 to W7D1), after which vidutolimod will be administered every 3 weeks (Q3W) (W10D1, W13D1, etc.). The first dose of vidutolimod may be administered subcutaneously or by IT injection at the discretion of the Investigator; all subsequent doses are planned to be administered by IT injection. The initial 7 doses of vidutolimod delivered on a weekly dosing schedule, must be completed before starting the Q3W vidutolimod dosing schedule.
2. Cemiplimab 350 mg IV infusion over 30 minutes (± 10 minutes) Q3W for the duration of the study (up to 2 years).

On visits where both study drugs are administered (W1D1 and Q3W thereafter), vidutolimod should be administered before cemiplimab.

Duration of treatment:

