Subjects will continue study treatment until they reach a reason for treatment or study discontinuation. Clinically stable subjects may continue study treatment beyond RECIST v1.1 progression based upon Investigator judgment of potential benefit. Study treatment may not continue beyond 2 years from initial dose of study treatment.

If a subject achieves and maintains a confirmed CR, treatment with vidutolimod or the combination of vidutolimod and cemiplimab may be discontinued at the Investigator's discretion once they meet both of the following criteria:

- Subject has been treated with both study treatments for at least 24 weeks.
- Subject has received at least 3 doses of both study treatments beyond the date of the initial CR

Subjects who discontinue vidutolimod or both vidutolimod and cemiplimab may not be retreated on this study with the previously discontinued treatment(s).

End of Study

The definition for End of Study (Trial) is the date of global last subject's last visit (100 days \pm 7 days after the last dose of study drug: vidutolimod or cemiplimab), or the date of withdrawal from the study, or lost to follow-up (ie, the study subject can no longer be contacted by the investigator) whichever comes first. The sponsor has the right to terminate the study at any time.

Reference therapy, dosage and mode of administration:

Not applicable.

Criteria for evaluation:**Efficacy:**

Disease status will be assessed by CT or MRI and other appropriate measures according to the Schedule of Assessments. Calipers and photographs containing a ruler may be used to facilitate measurement of superficial cutaneous tumors. Objective responses will be assessed by the Investigator according to RECIST v1.1. Other endpoints include PFS, DOR, best overall response, and OS.

Translational Assessments:

- Quantification of the concentration of selected cytokines and chemokines from blood of subjects obtained at time points specified in the Schedule of Assessments.
- Analysis of CD3⁺ and CD8⁺ T cell infiltrates or other multi-parameter assessment of the tumor microenvironment in tumor tissue obtained via fresh biopsy or from archival tumor tissue, and correlation with antitumor activity.

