9. Known additional malignancy that is progressing or required active treatment within the past 3 years. Exceptions include cancers that have undergone potentially curative therapy,

e.g. basal cell carcinoma of the skin, squamous cell carcinoma of the skin, localized prostate cancer with prostate-specific antigen level below 4.0 ng/mL, in situ cervical cancer on biopsy or a squamous intraepithelial lesion on Papanicolaou smear, and thyroid cancer (except anaplastic), in situ breast cancer, and adjuvant hormonal therapy for breast cancer > 3 years from curative-intent surgical resection.

10. Active autoimmune disease that required systemic treatment in past 2 years; replacement therapy is not considered a form of systemic treatment.
11. Untreated, symptomatic, or enlarging central nervous system (CNS) metastases or carcinomatous meningitis (including leptomeningeal metastases from solid tumors).
12. Prior allogenic tissue/solid organ transplant.
13. Active infection requiring systemic therapy.
14. Known or suspected active infection with severe acute respiratory syndrome coronavirus 2 (SARS-CoV-2).
15. Known or suspected active infection with human immunodeficiency virus, hepatitis B virus, or hepatitis C virus (testing is not required unless suspected).
16. Received a live virus/attenuated vaccination within 30 days before first dose of study treatment on W1D1.
17. Received blood products (including platelets or red blood cells) or colony stimulating factors (including granulocyte colony stimulating factor, granulocyte/macrophage colony stimulating factor, or recombinant erythropoietin) within 3 weeks before the W1D1 visit.
18. History of permanent discontinuation of cemiplimab due to infusion reactions or hypersensitivity to the investigational agents or their excipients.
19. Any concurrent uncontrolled illness, including mental illness or substance abuse, which in the opinion of the Investigator would make the subject unable to cooperate or participate in the study.
20. Participation in another clinical study of an investigational anticancer therapy or device within 30 days before first dose of study treatment on W1D1. Note: Participation in the follow-up phase (receiving no study treatment) of a prior study is allowed.
21. Requires prohibited treatment (i.e. non-protocol specified anticancer pharmacotherapy, surgery, or conventional radiotherapy) for treatment of malignant tumor.

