#### **3.1. Full Analysis Set (FAS)**

The full analysis set (FAS) includes all enrolled patients who received any study drug. Efficacy endpoints will be analyzed using the FAS.

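### Section 3.8 bars, with no exception, the adjuvant hormonal therapy that exclusion criterion 9 tolerates

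*Protocol*

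**What the plan says.** Protocol Section 3.6, criterion 9, excludes a known additional cancer that is advancing or has needed active treatment in the preceding 3 years. It then lists exceptions, the last being "adjuvant hormonal therapy for breast cancer > 3 years from curative-intent surgical resection". The synopsis carries the same exception under Key Exclusion Criteria, so it is not a slip in one place.

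Protocol Section 3.8 opens its list of prohibited medications with this rule: "Concurrent systemic anticancer therapy with agents other than the combination study drug therapy (vidutolimod + cemiplimab) is not allowed at any time" during the study. The same bullet grants one relaxation: "Topical anticancer therapy agents are allowed provided they are not used for the target or non-target lesions". Elsewhere the section allows supportive-care medication and certain uses of corticosteroids. Section 3.9 repeats the supportive-care allowance and refers back to Section 3.8.

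Criterion 21 of Section 3.6 also bears on the point. It excludes a subject who "Requires prohibited treatment (i.e. non-protocol specified anticancer pharmacotherapy, surgery, or conventional radiotherapy) for treatment of malignant tumor".

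**The concern.** The two rules give opposite signals for one kind of subject: someone with a study cancer who also had a breast cancer resected more than 3 years ago and still takes adjuvant hormonal therapy for it. Criterion 9 does not turn this person away. Section 3.8, read as written, does not let the person keep taking the drug.

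The stakes are patient care and uniform conduct. A site that follows Section 3.8 to the letter has to withdraw a drug whose purpose is to prevent recurrence of another cancer, or leave it in place and log a prohibited-medication deviation. A more cautious site may decline to enrol the subject, which empties the criterion 9 exception for that person. Different sites in a multicenter study can reach different answers from the same text. The protocol lists all deviations by subject (Section 8.4.7), and the SAP summarizes important ones by cohort (SAP Section 5.3), so inconsistent reading can also reach the deviation reporting.

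**Working it through.** The plan states no figure on this point, so the check is mainly a comparison of texts.

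**1. Does the criterion 9 exception reach a subject still on therapy?** The word *ongoing* does not appear. Two features point that way:
- The exception is needed only where hormonal therapy could count as active treatment in the last 3 years, that is, where it is current or was recently stopped.
- The 3-year interval is measured from the resection. Nothing requires the therapy to have ended.

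Current users therefore fall within it. Subjects who have finished therapy also fall within it, and for them there is no conflict.

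**2. Does the Section 3.8 rule reach adjuvant hormonal therapy?** The protocol does not define systemic anticancer therapy, but the literal reading has support:
- Criterion 9 needed a carve-out for this therapy, which suggests that the protocol regards it as treatment of a malignancy.
- The rule is not confined to the cancer being studied. The authors knew how to confine a rule in that way: the last bullet of the same list bars "Complementary medications to treat the disease under study (e.g. herbal supplements or traditional Chinese medicines"), and criterion 2 has the same limit.
- The only hormonal agent named as allowed is megestrol, and only for anorexia.

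**3. Does any allowance rescue the subject?**
- Topical agents: no, the therapy is systemic.
- Supportive care: no, the purpose is prevention of recurrence.
- Corticosteroid exceptions: not relevant.
- Section 3.9: adds no further exception.

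**4. Does criterion 21 settle it?** There are two cases:
- If it covers adjuvant hormonal therapy, the subject is screened out and the criterion 9 exception is void for current users.
- If it does not, because adjuvant treatment after curative resection is not treatment of an existing tumor, the subject enrols and meets the Section 3.8 rule.

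The text needs correcting in either case, so the finding does not depend on how criterion 21 is read.

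**5. Size.**
- Time without the drug: the synopsis says "Study treatment may not continue beyond 2 years from initial dose of study treatment", so the on-treatment maximum is 2 × 12 = 24 months.
- A wholly literal reading of the rule would run on into post-treatment follow-up, capped at 18 months per subject (Section 6.6), giving 24 + 18 = 42 months before any gap between the two periods. However, Section 6.6 and the survival follow-up questions in Section 6.1.6 both foresee new cancer treatment after study drug stops. The 24 months is the period where the rule plainly applies.
- Analysis set: the SAP says "The full analysis set (FAS) includes all enrolled patients who received any study drug". A treated subject stays in whether the hormonal therapy is stopped or continued, so the change in the response-rate denominator is 0.
- Planned enrolment: 9 cohorts × about 25 = about 225, unchanged. A subject refused at screening never enters the set, but the enrolment target is the same.

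**The case against.** The best counter-argument is that no contradiction has been shown. Criterion 9 looks back at cancer history, and a subject who took hormonal therapy in the last 3 years and stopped before entry uses the exception without touching Section 3.8. Passing one criterion is also not permission to take a drug: Section 6.1.2 requires every criterion to be met, and concomitant medication is governed separately. The prohibition rests on an undefined term. Criterion 21 speaks of treating a malignant tumor, and the SAP ends its on-treatment period at new systemic therapy for the patient's tumor (SAP Section 10); both suggest a narrower aim. A sensible site would let the specific exception prevail over the general rule, or would ask the sponsor. Few subjects are involved and no analysis changes.

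Some of this stands. The number affected is unknown and probably small, the key term is undefined, and the sponsor may have meant completed therapy only. None of it removes the problem. The exception is not limited to completed therapy, the first bullet lacks the limit found elsewhere in its own list, and a site has to guess which text governs. Section 3.8 requires Medical Monitor consultation for adrenal insufficiency, and Section 3.8.2 requires it for palliative procedures, but neither offers that route for this therapy.

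**Conclusion.** The concern holds. For a subject still on adjuvant hormonal therapy more than 3 years after curative-intent breast surgery, criterion 9 and Section 3.8 conflict as written, and no other allowance resolves it. This rests on two ordinary readings: that the exception includes current users, and that adjuvant hormonal therapy counts as systemic anticancer therapy.

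The consequence for an affected subject can be serious, but there are probably few such subjects; the documents give no count and none is estimated here. There is no effect on sample size, error rates or the response-rate analysis. The case for acting is patient safety and consistent site conduct, set against almost no cost.

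**What to change.** Add to the first bullet of Section 3.8: *except adjuvant hormonal therapy for a prior breast cancer permitted under exclusion criterion 9*. Add to criterion 21 that such therapy is not a prohibited treatment. Subjects admitted under criterion 9 then keep their therapy and generate no deviation. The synopsis already carries the criterion 9 exception and needs no change.

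If the sponsor intended the exception for completed therapy only, the alternative is to say so in criterion 9, in both Section 3.6 and the synopsis, and leave Section 3.8 alone. Either route removes the ambiguity.

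The preferred change costs half a sentence in Section 3.8 and one in criterion 21, with no added procedures, subjects or analyses.

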3.8.1. Vaccinations

Subjects should not have received a live virus/attenuated vaccination within 30 days before first dose of study treatment on W1D1.

Given the potential for injection site reactions and flu-like symptoms, vaccination with a viral vector or mRNA vaccine should not be performed within 72 hours of vidutolimod injection.

COVID-19 vaccination, either as an initial series or as a booster dose, received during the study, will be treated as a concomitant medication. As noted, administration of a COVID-19 vaccination should be separated from the time of administration of the investigational product (at least 72 hours, ideally by at least 1 week) in order to avoid confounding the effects (eg, adverse effects) of the vaccine/booster with the effects of study drug.

3.8.2. Concomitant Procedures

Palliative radiotherapy or palliative surgery may be allowed after Medical Monitor consultation to ascertain whether clinical progression has occurred. If the lesion(s) targeted for palliation are target lesions, then the anatomic site requiring palliation must be assessed for disease status.

3.9. Concomitant Medications

IMPORTANT: Prophylactic medications are required prior to vidutolimod administration, as described in Section 4.1.1.1. Prophylactic medications administered before and after vidutolimod dosing will be collected in the electronic data capture (EDC) for each visit.

Allowed concomitant medications include those intended solely for supportive care (i.e. antiemetics, analgesics, megestrol acetate for anorexia).

Prohibited treatments are described in Section 3.8.

4. TREATMENT OF SUBJECTS

4.1. Administration of Study Drugs

All subjects will receive vidutolimod injection followed by cemiplimab administered IV according to the dosing schedules shown in the Schedule of Assessments ([Table 1](#)).

Table 3: Study Interventions Administered

Intervention Name	Vidutolimod	Cemiplimab
Dose Formulation	Sterile solution	Sterile solution
Unit Dose Strength(s)	5 mg/mL	50 mg/mL
Dosage Level(s)	See Section 4.1.1	See Section 4.1.2
Route of Administration	SC or IT	IV
Use	experimental	experimental
IMP and axMP	IMP	IMP
Sourcing	Provided centrally by the sponsor	Provided centrally by the sponsor

4.1.1. Vidutolimod

Subjects will receive vidutolimod 10 mg weekly for 7 doses (W1D1 to W7D1), after which vidutolimod will be administered by IT injection Q3W (W10D1, W13D1, etc.). The first dose of vidutolimod may be administered SC or by IT injection, at the discretion of the Investigator; all subsequent doses are planned to be administered IT. On visits where both study drugs are administered, vidutolimod should be administered before cemiplimab. There is no specified waiting period between the end of vidutolimod administration and the initiation of cemiplimab infusion. Vidutolimod should be administered up to 2 years or until a reason for treatment discontinuation is reached ([Section 3.2](#)).

4.1.1.1. Required Prophylaxis Before and After Vidutolimod Injection

To reduce the incidence and severity of symptoms associated with vidutolimod injection, prophylaxis is required. All recommended prophylaxis should be administered before initiation of the vidutolimod injection. The medications are recommended for oral administration, but IV is acceptable at the discretion of the Investigator. There is no mandatory waiting period between the end of prophylaxis and the start of the vidutolimod injection.

The optimal recommended regimen that has been effective for the treatment of vidutolimod associated AEs should include all of the following components:

- Intravenous fluids (e.g. approximately 1000 cc IV normal saline). The rate, volume, and substitution fluids are at the Investigator's discretion.
- Antipyretics (e.g. acetaminophen 1000 mg and a non-steroidal anti-inflammatory agent such as indomethacin 50 mg or ibuprofen 600 to 800 mg)
- Antiemetics (e.g. ondansetron 8 mg)
- Antihistamine (e.g. diphenhydramine 50 mg, with or without an H2-antagonist)

- Recommended hydrocortisone 25 mg at the Investigator's discretion. Subjects with adrenal insufficiency should be treated with stress dose steroids as described in Section 4.1.1.1.1.

It is also highly recommended to continue to administer IV fluids during the observation period immediately following the vidutolimod injection, rather than waiting to initiate fluids if hypotension is detected. Antipyretics, antiemetics, and antihistamines may be repeated at the Investigator's discretion.

Each medication given prophylactically before and after vidutolimod dosing must be recorded separately and for each visit.

4.1.1.1. Prophylaxis for Subjects with Adrenal Insufficiency

Subjects with adrenal insufficiency are at increased risk for moderate to severe AEs such as hypotension, which may occur within 1 to 4 hours after vidutolimod injection but may also occur outside this window. Subjects with known adrenal insufficiency may be allowed in the study.

At Screening, subjects previously treated with a CTLA-4 blocking antibody, subjects with clinical symptoms and/or laboratory findings suggesting risk for adrenal insufficiency, or subjects receiving corticosteroids with daily doses > 5 mg and ≤ 10 mg of prednisone equivalent for > 2 weeks should undergo diagnostic tests for adrenocorticotrophic hormone (ACTH) and morning cortisol, and/or high-dose ACTH stimulation test (preferred testing method), if clinically indicated, via local laboratory, unless the diagnosis of adrenal insufficiency had been previously established.

All subjects with adrenal insufficiency must receive prophylactic stress-dose steroids (e.g. 50 to 100 mg hydrocortisone or equivalent orally every 8 hours) before and for 24 to 48 hours after each vidutolimod injection.

4.1.1.2. Observation Following Vidutolimod Dosing

Subjects must be observed for at least 4 hours following each of the first 6 injections (W1D1 to W6D1). Beginning with the seventh injection (W7D1), the observation period may be reduced to a minimum of 1 hour following injection at the Investigator's discretion based on the AE profile of the individual subject.

4.1.1.3. Vidutolimod Injections

Refer to [Appendix A](#) and the Intratumoral injection manual.

4.1.1.3.1. Tumor Selection

Cutaneous, SC, and/or nodal tumors that are visible, palpable, or detectable by ultrasound or CT guidance are acceptable for IT injection. Systematic support from interventional radiology is required in case of IT injections to visceral lesions. For subjects who have lesions that are not externally visible, guidance on tumor selection and IT injections is included in a separate procedure manual.

Vigilance should be used when selecting lesions for injection that are in close proximity to critical structures (e.g. major airways).

- Special attention and judgment should be exercised before injection of a lesion in the following areas: the “mask areas” of the face (central face, eyelids, eyebrows, periorbital nose, lips [cutaneous and vermillion], chin, mandible, preauricular and postauricular skin/sulci, temple, ear, genitalia, hands, and feet).
- Unsuitable sites for intratumoral or subcutaneous injection would include, for example, the palm of the hand or the sole of the foot.
- Tumors should be at least 0.5 cm in longest diameter and need not be the largest lesion. A visceral tumor may be injected with the use of interventional radiology if, in the opinion of the Investigator and after discussion with the Medical Monitor, it is considered to be the most appropriate site for IT injection. A preferred tumor for IT injection is an accessible lesion that is most rapidly progressing in the judgment of the Investigator. Injected lesions may or may not be target lesions.
- It is allowed to inject all palpable lesions, even if they are all target lesions.
- It is allowed to biopsy injected lesions.

When more than 1 tumor is amenable to IT injection, the Investigator may inject up to 3 tumors per vidutolimod treatment visit. The total dose of vidutolimod may be divided across the tumors at the Investigator’s discretion, and the volume injected into each tumor must be recorded.

- The same tumor(s) should be injected with each individual vidutolimod administration, if possible.

If an injected tumor is clearly decreasing in size and another accessible noninjected tumor is not, then the Investigator may divide the vidutolimod dose between the 2 tumors or switch from injecting the regressing tumor to injecting the nonresponding (or growing) tumor. Subjects with metastatic disease who have regression of all injectable lesions, or who have an injection site reaction that precludes injection of the tumor, should receive vidutolimod SC near an original tumor (peritumoral) or in the area of the draining lymph nodes (see [Appendix A](#)).

